3. A monthly urine pregnancy test must be performed by all women of child-bearing potential between the three monthly visits at the investigational site. Urine pregnancy tests may be performed at the investigational site or at home. Test results performed at home should be recorded in a patient diary and brought to each scheduled visit for the site to review. If a test result indicates a pregnancy, the patient must contact the investigator immediately.
4. Only required for Early Discontinuation due to lack of response / loss of response.
5. Same tube will be used for RQ PCR CCI [REDACTED]
6. For patients who are not in MMR at week 48 and for patients losing the response after week 48 assessments up to week 108 and who may benefit from a dose escalation, CCI [REDACTED].
7. Samples to be collected before first dose and 2 to 4 hours post dose.
8. After week 48, the ECG assessments will be done at week 60, week 84, week 108 and week 132 for patients on standard dose (80mg q.d. and 40mg b.i.d.).
9. For patients with dose escalation ECG assessment to be conducted: at dose escalation visit (pre-dose and two hours post-dose), two weeks post-dose escalation, 3 months post-dose escalation, 6 months post-dose escalation, 6 monthly thereafter. Please refer to [Section 8.4.3](#) for more information.
10. Personal and family history of the following conditions: Coronary artery disease, Hyperlipidaemia, Type 1 diabetes mellitus, Type 2 diabetes mellitus, Hypertension, medication taken for hypertension, Myocardial infarction or Cerebrovascular accident will be collected at screening. History of smoking, physical activity and diet will be collected at screening and end of treatment.
11. Week 24 echocardiogram can be performed within a window of +/- 4 weeks of the visit
12. After week 48, PRO assessment will be done every 24 weeks up to week 120 (i.e. these assessments will be completed at week 72, week 96 and week 120).
13. Safety follow-up may be done on site or via phone call with patient. The safety follow-up to be completed 30 days from the last dose of study treatment.

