8.4.3.1 Cardiac imaging - Echocardiogram

Echocardiograms will be performed to monitor cardiac safety. Assessments are scheduled at screening/baseline, Week 24 (+/- 4 weeks) and end of treatment visit. The echocardiogram will be performed and evaluated locally. Any clinically significant findings will be collected and reported in the database (i.e. reported as adverse events).

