9.1 Discontinuation from study treatment and from study

9.1.1 Discontinuation from study treatment

Discontinuation of study treatment for a participant occurs when study treatment is permanently stopped for any reason (earlier than the planned completion of study drug administration) and can be initiated by either the participant or the investigator.

The investigator must discontinue study treatment for a given participant if, he/she believes that continuation would negatively impact the participant's well-being.

Study treatment must be discontinued under the following circumstances:

- Participant/guardian decision
- Pregnancy
- Use of prohibited treatment. Refer to [Section 6.2.2](#).
- Any situation in which continued study participation might result in a safety risk to the participant
- In the case of certain adverse events and re-occurrence of adverse events (see [Table 6-4](#))
- Major Protocol Deviation, or any other protocol deviation that results in a significant risk to the patient's safety.

In addition to the general discontinuation criteria, the following study specific criteria will also require discontinuation of study treatment:

- In the event of treatment failure the patient should be discontinued from the study treatment. The ELN criteria 2020 do not make provisions for treatment failure in 3rd line however they define that a level of BCR-ABL1 > 1% IS and failure to achieve CCyR is not sufficient for optimal survival. The following events will constitute 'treatment failure':
 - BCR-ABL1 >1% IS at 48 weeks after initiation of therapy or no complete cytogenetic response at 48 weeks.

- Patients fulfilling treatment failure criteria above but without alternative treatment options may however be continued on study drug if in the investigators opinion they are obtaining benefit from the drug. Patients with BCR-ABL 1 greater than 10% after 48 weeks of treatment or patients with signs of progression to AP and BC must however be discontinued.
- Patients with newly emerging T315I mutation and lack or loss of response. While asciminib has known activity against CML with additional T315I mutation, the recommended dose of 200 mg BID for the treatment of T315I is not in use in the study. In case a patient demonstrates a new T315I mutation on asciminib, patients should not continue in the study.

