2.1 Data analysis general information

The planned analyses will be performed by Novartis. SAS version 9.4 or later will be used to perform all data analyses and to generate tables, figures and listings.

No formal interim analysis is planned for this trial. The following analyses are planned as detailed below.

- 48-week primary analysis: Formal testing of the primary endpoint will be performed. Analyses of other efficacy endpoints at and by week 48 and safety analyses will also be performed.
- 96-week analysis: Analyses of efficacy endpoints at and by week 96 and safety analyses will be performed.
- End of study treatment analysis is similar to the 96-week analysis without formal statistical testing. All efficacy and safety analyses will be included.

Except where categorically stated, all analyses, including the primary analysis will be conducted on **all** participant data (excluding the additional subjects who were intolerant to the last TKI and were in MMR at baseline). The purpose of having two randomized groups is not for comparison, but to provide data on different dosing regimens. Randomization is only used to have a balance in the allocation of treatment into either asciminib 40 mg b.i.d. or 80 mg q.d.

Data included in the analyses

The analysis data cut-off dates for the planned analyses are:

- 48-week Primary analysis: After all randomized subjects have been on study treatment for 48 weeks or discontinued earlier, i.e., LPFT + 48 weeks.

- 96-week analysis: After all randomized subjects have been on study treatment for 96 weeks or discontinued earlier, i.e., LPFT + 96 weeks.
- End of study treatment analysis: 30 days after the EOsT. (Note: After the study treatment period, every effort will be made to continue provision of the study treatment to subjects who in the opinion of the investigators are still deriving clinical benefit through alternative options if asciminib is not commercially available).

All statistical analyses will be performed using all data collected in the database up to the respective data cut-off date. All data with an assessment date or event start date (e.g. vital sign assessment date or start date of an adverse event) prior to or on the cut-off date will be included in the analysis. Any data collected beyond the cut-off date will not be included in the analysis and will not be used for any derivations.

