1. ***pre-treatment period:*** from day of subject’s informed consent to the day before first administration of study treatment
2. ***on-treatment period:*** from date of first administration of study treatment to 30 days after date of last administration of study treatment (including start and stop date).
3. ***post-treatment period:*** starting at day 31 after last administration of study treatment.

If dates are incomplete in a way that clear assignment to pre-, on-, post-treatment period cannot be made, then the respective data will be assigned to the on-treatment period.

Safety summaries (tables, figures) on the corresponding Safety set include only data from the on-treatment period with the exception of baseline data which will also be summarized where appropriate (e.g. change from baseline summaries). In particular, summary tables for adverse events (AEs) will summarize only on-treatment events, with a start date during the on-treatment period. In addition, a separate summary for death will be provided.

However, all safety data (including those from the pre-treatment and post-treatment) will be listed and flagged as appropriate.

Efficacy summaries on the FAS and FAS 2 (apart from OS and PFS) include data from baseline up to either the last assessment on or before the End of Treatment (EoT) visit or before or on treatment failure, whichever is the earliest.

The efficacy assessments collected post-treatment failure or post-EoT visit are not included in any efficacy analyses (except for OS and PFS analyses). However, they will be listed and flagged as appropriate.

Windows for multiple assessments

Data such as molecular response, cytogenetic response collected over time (including unscheduled visits) will be summarized by scheduled time point. As subjects do not always adhere to the visit schedule, visits will be remapped according to visit windows defined in Tables 2-1 to Table 2-3 of this document to enable by-visit analysis. Only those protocol-defined visits will have the visit window defined. Each assessment (including the end of treatment assessment), either scheduled or unscheduled, will have a mapped visit assigned, as long as study day is available, according to the defined visit window up to the date with data included.

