2.7.4 Other safety data

2.7.4.1 ECG and cardiac imaging data

ECG

12-lead ECGs including PR, QRS, QT, QTcF, and RR intervals will be obtained locally for each subject during the study. ECG data will be read and interpreted locally.

The echocardiogram will be performed and evaluated locally to assess the left ventricular ejection fraction (LVEF).

Data handling

The average of the triplicate ECG parameters at each time point will be used in the analyses.

For unscheduled visits, ECGs that are reported on the same day and within 30 minutes apart from each other will be assumed to be sequential ECGs and thus will be used to compute the mean of the ECG parameters.

Unscheduled ECG measurements will not be used in computing the summary statistics for change from Baseline at each post-baseline time point. However, they will be used in the outlier analyses (e.g. QTc > 450 ms, > 480 ms, or > 500 ms at any time point, or an increase from Baseline in QTc > 30 ms or > 60 ms). End of treatment ECG measurements for discontinued subjects will be considered as an unscheduled measurement in case it occurs outside a scheduled visit.

Data analysis

The number and percentage of subjects with notable ECG values will be presented for the corresponding Safety set (SAF, SAF 2). Notable values are defined below:

- QT, QTcF
 - New value of > 450 and \leq 480 ms
 - New value of > 480 and \leq 500 ms
 - New value of > 500 ms
 - Increase from Baseline of > 30 ms to \leq 60ms
 - Increase from Baseline of > 60 ms
- HR
 - Increase from baseline >25% and to a value > 100 bpm
 - Decrease from baseline >25% and to a value < 50 bpm
- PR
 - Increase from baseline >25% and to a value > 200 ms
 - New value of > 200 ms
- QRS
 - Increase from baseline >25% and to a value > 120 ms
 - New values of QRS > 120 ms

A listing of all ECG assessments will be produced and notable values will be flagged. A separate listing of only the subjects with notable ECG values will also be produced. In each listing the assessments collected during the post-treatment period will be flagged.

Change from baseline ECG parameters by timepoint will also be summarized.

A listing of all LVEF assessments will be produced. In the listing, the assessments collected outside of on-treatment period will be flagged.

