A summary table with descriptive statistics for LVEF at different timepoints (screening/baseline, Week 48 (+/- 4 weeks) and end of treatment visit) and for change from baseline will be presented. A shift table for LVEF categories ($\leq 40\%$, 41-49%, $\geq 50\%$) at baseline versus worst value on treatment will also be presented.

ECG assessment needs are similar for all subjects up to week 48.

For subjects with dose escalation, ECG assessments will be performed at:

- on the day of dose escalation (pre-dose and between 2h to 3h post-dose ECGs are required),
- two weeks post-dose escalation,
- at next 2 quarterly visits (at 3 and 6 months post-dose escalation),
- every 6 months thereafter.

The above described analyses for ECG data will also be performed separately for a) subjects by dose escalation status (with or without dose escalation) and for b) only for subjects with dose escalation (prior to and after dose escalation).

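### The SAP summarises on-treatment LVEF at Week 48, but the protocol schedules its only mid-treatment echocardiogram at Week 24

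*SAP*

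**What the plan says.** **LVEF.** SAP 2.7.4.1 specifies "A summary table with descriptive statistics for LVEF at different timepoints (screening/baseline, Week 48 (+/- 4 weeks) and end of treatment visit", with a change-from-baseline summary at the same time points. The same section provides a three-category shift table from baseline to the worst value on treatment (at most 40%, 41-49%, at least 50%), and also states: "A listing of all LVEF assessments will be produced".

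Protocol 8.4.3.1 gives a different mid-treatment time: "Assessments are scheduled at screening/baseline, Week 24 (+/- 4 weeks) and end of treatment visit". Footnote 11 to the assessment schedule (Protocol Table 8-1) agrees with that section: "Week 24 echocardiogram can be performed within a window of +/- 4 weeks of the visit". Protocol 8.4.3.1 adds: "Any clinically significant findings will be collected and reported in the database (i.e. reported as adverse events".

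For the 48-week analysis, SAP 2.1 states: "Analyses of other efficacy endpoints at and by week 48 and safety analyses will also be performed". It plans safety analyses at the 96-week cut as well. SAP section 4, which is the place to declare changes from the protocol's analyses, is marked not applicable.

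**PRO.** SAP 2.1.1 says that "visits will be remapped according to visit windows defined in Tables 2-1 to Table 2-3 of this document". In Table 2-3 the last MDASI-CML window, EOT (Week 144), runs from Day 926 to Day 1009, with Day 1 as the date of randomization. Protocol section 8 allows the EOT visit 7 days either side of its designated date.

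**The concern.** The SAP's list of LVEF time points matches the protocol's in every respect except the week number. No passage in either document schedules an echocardiogram at Week 48. A programmer who follows the SAP literally would build a mid-treatment row for a visit with no planned echo, and would leave the planned echo out of the table.

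What would be lost is specific. The by-visit table is the only planned numerical summary of LVEF and its change from baseline. Patients still on treatment at the 48- or 96-week cut have had no end-of-treatment echo, so Week 24 is their only scheduled post-baseline measurement. The shift table is a coarse substitute: a fall from 65% to 52%, to take an illustration, stays within its top category.

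The PRO window raises a similar but smaller question: whether a questionnaire completed at a compliant but late final visit has any row to go to.

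**Working it through.** **1. LVEF windows.** Inputs: target day for Week k = 7k + 1 (SAP 2.1.1; the protocol schedule also shows Days 169 and 337); 4 weeks = 28 days.

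| Source | Target day | +/- 28 days |
|---|---|---|
| Protocol, Week 24 | 24 × 7 + 1 = 169 | 141 to 197 |
| SAP, Week 48 | 48 × 7 + 1 = 337 | 309 to 365 |

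Distance between the windows: 309 − 197 = 112 days.

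Footnote 11 could be read as counting the 4 weeks from the actual visit, which may itself move by 7 days. On the most generous reading, with both windows stretched towards each other, the protocol window ends at 169 + 7 + 28 = 204 and the SAP window starts at 337 − 7 − 28 = 302. The distance is then 302 − 204 = 98 days. A scheduled Week 24 echo cannot fall in the SAP's Week 48 window on either reading.

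**2. Who has what at the data cuts.** Scheduled echoes are at baseline, Week 24 and end of treatment. A patient on treatment at the 48- or 96-week cut has not reached end of treatment. The scheduled post-baseline LVEF is therefore the Week 24 value alone, and the SAP table gives it no row.

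**3. Where the Week 24 value does appear.** It appears in the listing of all LVEF assessments, in the shift table as a candidate for the worst value, and among adverse events if clinically significant.

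**4. PRO window.** The SAP's general rule sets an upper limit at the target day plus the integer part of half the distance to the next target. For Week 120 this gives 841 + (1009 − 841)/2 = 841 + 84 = 925, as Table 2-3 states, so the EOT window opens at Day 926, also as stated. EOT has no next visit, and the table stops at the target day, 144 × 7 + 1 = 1009.

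The latest compliant EOT visit is 1009 + 7 = Day 1016, counted from Week 1 Day 1. If randomization and Week 1 Day 1 coincide, forms dated Day 1010 to 1016 map to no window. If the first dose comes d days after randomization, the latest compliant form falls on Day 1016 + d on the SAP's scale. With d of 1 or more, a form completed exactly on the designated date also falls outside.

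**The case against.** The strongest reply is that one wrong week number in one descriptive safety table does little harm. That largely stands. For a patient still on treatment at the interim cuts, the Week 24 echo is the only scheduled post-baseline value, so it would normally also be the worst value in the shift table. It is listed individually, and clinically significant findings are reported as adverse events. A reader might infer that the cardiac imaging data are lost or that LVEF safety goes unreported. The documents do not support that: only the by-visit descriptive row and its change from baseline are missing.

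A reader might also infer that the protocol lacks a Week 48 echo that the SAP expects. Nothing supports this. Protocol 8.4.3.1 and footnote 11 agree with each other, and the SAP declares no change. The mismatch lies in the SAP's analysis time point and gives no reason to alter the echo schedule.

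A third inference would be that early-discontinuation echoes have no defined row, or that they would fill the Week 48 row. Treatment failure under Protocol 9.1.1 includes "BCR-ABL1 >1% IS at 48 weeks after initiation of therapy or no complete cytogenetic response at 48 weeks", so some patients may well stop near that time. But the SAP table already has an end-of-treatment row, the SAP defines EOT at subject level, and the protocol schedule puts EOT and early discontinuation in one column. Those echoes belong in the end-of-treatment row. The absence of LVEF from SAP Tables 2-1 to 2-3 is not a gap either, because its window is given in 2.7.4.1 itself.

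On the PRO window, it is fair to say that the number of forms affected is unknown and may be small.

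**Conclusion.** The mismatch is confirmed and minor. Followed as written, SAP 2.7.4.1 gives a Week 48 LVEF row holding almost nothing but unscheduled echoes. It also leaves the scheduled Week 24 echo out of the only numerical by-visit summary of LVEF change. The windows are 112 days apart, or 98 on the most generous reading. The primary endpoint and its test are untouched.

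The conclusion rests on Protocol 8.4.3.1 and footnote 11. The echocardiogram row of Table 8-1 could not be read in the text available, but these two places agree on Week 24. That the SAP figure is a slip is an inference from the otherwise identical list of time points. The mismatch holds whether or not it is one.

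The PRO point is separate and also minor. Compliant late Week 144 forms have no window. The exact days affected depend on the interval between randomization and first dose, and the share of forms cannot be derived from the documents.

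**What to change.** In SAP 2.7.4.1, change the on-treatment LVEF analysis time point from Week 48 (+/- 4 weeks) to Week 24 (+/- 4 weeks), matching the protocol schedule. No rule for early-discontinuation echoes is needed.

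In SAP Table 2-3, make the upper limit of the EOT (Week 144) window open-ended: Day 926 or later, up to the EOT visit. A fixed limit of Day 1016 would be safe only if randomization and first dose always fall on the same day.

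The cost is one phrase and one table cell, with no new data or visits. If the relevant database is already locked, record both as changes to the planned analysis.

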8.4.3 Electrocardiogram (ECG)

A standard 12 lead ECG will be performed as described in [Table 8-6](#).

ECG assessment needs are similar for all patients up to week 48.

Patients dose escalating to 200 mg q.d. (as outlined in [Section 6.6.2](#)) must have ECG assessments performed:

- on the day of dose escalation (pre-dose and between 2h to 3h post-dose ECGs are required),
- two weeks post-dose escalation,
- at next 2 quarterly visits (at 3 and 6 months post-dose escalation),
- every 6 months thereafter.

Please refer to ([Table 8-6](#)) below for more details.

After the subject has rested approximately 5 minutes in a supine position, standard 12- lead ECGs must be obtained in triplicate with a recommended interval of 5 minutes between each ECG reading.

The preferred sequence of cardiovascular data collection during study visits is ECG collection first, followed by vital signs and then blood sampling. The Fridericia QT correction formula (QTcF) should be used for clinical decisions. The investigator must calculate QTcF if it is not auto-calculated by the ECG machine.

ECGs will be locally collected and evaluated. Interpretation of the tracing must be made by a qualified physician and documented on the ECG CRF page. Each ECG tracing should be labeled with the study number, patient initials (where regulations permit), subject number, date, and kept in the source documents at the study site.

Table 8-6 Local ECG collection plan

Week	Day	Time
Screening/Baseline	Day -28 to -1	3 serial, 12 lead ECGs
1		3 serial, 12 lead ECGs between 2h to 3h post-dose
2		3 serial, 12 lead ECGs between 2h to 3h post-dose
4		3 serial, 12 lead ECGs
12		3 serial, 12 lead ECGs
24, 48		3 serial, 12 lead ECGs
For patients not dose escalating: Week 60, 84, 108, 132		3 serial, 12 lead ECGs
For patients dose escalating: Dose escalation visit (Week 60 or Week 72, 84, 96, 108, 120)		3 serial, 12 lead ECGs pre-dose and between 2h to 3h post-dose
Two weeks post dose escalation visit (Week 62 or Week 74, 86, 98 110, 122)		3 serial, 12 lead ECGs
Twelve weeks post dose escalation visit (Week 72 or Week 84, 96, 108, 120, and 132).		3 serial, 12 lead ECGs
Twenty-four weeks post dose escalation visit (Week 84 or Week 96, 108, 120, 132 and EOT)		3 serial, 12 lead ECGs
EOT		3 serial, 12 lead ECGs
Unscheduled or Unplanned ECG		3 serial, 12 lead ECGs

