2.1.1 General definitions

Investigational drug and study treatment

Investigational drug, will refer to asciminib. No additional treatment beyond investigational drug is included in this trial.

Treatment groups

- Asciminib 40 mg b.i.d. (Subjects randomized to asciminib 40 mg b.i.d. at the beginning of the study)
- Asciminib 80 mg q.d. (Subjects randomized to asciminib 80 mg q.d. at the beginning of the study)

The standard dose for all subjects in this study is asciminib 40 mg b.i.d. or 80 mg q.d. For subjects not achieving MMR at 48 weeks or losing the response after the week 48 assessment up to week 108, a dose escalation to 200 mg q.d. may be considered per investigator decision.

Date of end of study treatment (EOsT)

The EOsT date is the date that the study treatment is ended for the entire study. On this date, subjects are treated for at maximum 144 weeks, unless subjects have discontinued study treatment earlier.

Date of first administration of study treatment

The date of first administration of study treatment is derived as the first date when a non-zero dose of study treatment was administered as per the Study Treatment electronic case report form (eCRF). The date of first administration of study treatment will also be referred as start of study treatment.

The date of first administration of study treatment is the same as the date of first administration of investigational drug.

Start Date of dose escalation

The start date of dose escalation is derived as the first date when a subject had dose escalated to 200 mg q.d. of study treatment as per the Subject Status Dose Escalation case report form (eCRF).

Date of last administration of study treatment

The date of last administration of study treatment is defined as the last date when a non-zero dose of study treatment was administered as per Study Treatment eCRF.

The date of last administration of study treatment is the same as the date of last administration of investigational drug.

Study day

The study day, describes the day of the event or assessment date, relative to the reference start date.

The study day is defined as:

- The date of the event (visit date, onset date of an event, assessment date, etc.) – reference start date + 1 if event is on or after the reference start date;
- The date of the event (visit date, onset date of an event, assessment date, etc.) – reference start date if event precedes the reference start date.

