The reference start date for safety assessments (e.g. adverse event onset, laboratory abnormality occurrence, vital sign measurement, dose interruption, etc.) is the start of study treatment.

The reference start date for all other, non-safety assessments (e.g. molecular response, disease progression, ECOG performance status, patient reported outcomes (PRO), etc.) is the date of randomization.

The reference start date for dose escalation (200 mg q.d.) is the date when a subject starts first escalated dose.

The study day will be displayed in the data listings. If an event starts before the reference start date, the study day displayed on the listing will be negative.

Time unit

A year length is defined as 365.25 days. A month length is 30.4375 (=365.25/12) days. If duration is reported in months, duration in days will be divided by 30.4375. If duration is reported in years, duration in days will be divided by 365.25.

A week length is defined as 7 days. If duration is reported in weeks, duration in days will be divided by 7.

Baseline for the treatment period

For efficacy evaluations, the last non-missing assessment, including unscheduled assessments on or before the date of randomization is taken as “baseline” value or “baseline” assessment. In the context of baseline definition, the efficacy evaluations also include PRO and performance status.

For safety evaluations, the last available assessment, including unscheduled assessments before the date of start of study treatment is taken as “baseline” assessment.

For pre-dose electrocardiogram (ECG), the last available assessment before the treatment start date is used for baseline.

For ECGs requiring triplicate measures per time point, the average of these measurements will be reported by sites in eCRF baseline.

For mutations, the screening/baseline assessment is taken as “baseline” assessment.

In rare cases where multiple laboratory measurements meet the baseline definition, with no further flag or label that can identify the chronological order, then the following rule should be applied: If values are from central and local laboratories, the value from central assessment should be considered as baseline.

If subjects have no value as defined above, the baseline result will be missing.

On-treatment assessment/event and observation periods

For adverse event reporting the overall observation period will be divided into three mutually exclusive segments:

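### The after-escalation ECG tables use only the pre-treatment baseline, so no within-subject change for the step to 200 mg is planned, although a pre-dose ECG is taken on the escalation day

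*SAP*

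**What the plan says.** SAP 2.1.1 sets the baseline for all safety data before treatment begins: "For safety evaluations, the last available assessment, including unscheduled assessments before the date of start of study treatment is taken as" the baseline assessment. For ECGs it adds: "For pre-dose electrocardiogram (ECG), the last available assessment before the treatment start date is used for baseline". Start of treatment is "derived as the first date when a non-zero dose of study treatment was administered", which is the first dose at 80 mg daily and not the first dose at 200 mg.

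SAP 2.1.1 also gives a date for escalation: "The reference start date for dose escalation (200 mg q.d.) is the date when a subject starts first escalated dose". That sentence belongs to the definition of study day. The baseline paragraph does not take it up.

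SAP 2.7.4.1 builds its ECG summaries on this baseline. "Change from baseline ECG parameters by timepoint will also be summarized", and the notable QT/QTcF classes include "Increase from Baseline of > 30 ms to" 60 ms and a further class above 60 ms. The same section then repeats these analyses by escalation status and, separately, "only for subjects with dose escalation (prior to and after dose escalation". It names no baseline for the repeat.

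Protocol 8.4.3 requires ECGs "on the day of dose escalation (pre-dose and between 2h to 3h post-dose ECGs are required". Table 8-6 makes them triplicate, and SAP 2.7.4.1 restates the requirement. No analysis uses the pre-dose reading as a reference.

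**The concern.** For the escalated period a reader wants to know what happens to the ECG when the daily dose goes from 80 mg to 200 mg. The protocol escalates at Week 60 at the earliest, so a change measured from the pre-treatment ECG spans at least about 60 weeks of earlier treatment as well. The measurement that marks the step, the pre-dose triplicate on the escalation day, is collected but is not a reference for anything.

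This matters more than usual because earlier experience with this regimen is thin. Protocol 4.2 reports 12 patients treated at 200 mg q.d. It also relies on data at total daily doses up to 400 mg and on exposure-safety modelling, but the safety endpoints it names for that modelling do not include QTcF.

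There is a smaller gap beside it. Escalation start is recorded as a date, and the SAP does not say whether that day's pre-dose ECG belongs to the period before or after escalation. A split by date alone could place it in the 200 mg period.

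**Working it through.** The plan states no figure on this point, so there is none to reproduce. The check is a reading of the definitions, followed by an illustration under stated assumptions.

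**How old the baseline is.** Table 8-6 schedules the Week 1 ECG 2 to 3 hours after dosing, so the last ECG before treatment is normally the screening one (Day -28 to -1). Escalation is possible from Week 60 (Protocol 6.6.2) to Week 120 (SAP 1.1). At escalation the baseline ECG is therefore about 60 to 120 weeks old, plus up to 4 weeks of screening.

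**What the change contains.** Let B be the study baseline, P the pre-dose mean on the escalation day, and A a reading after escalation. Then

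A - B = (P - B) + (A - P).

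Write d for the mean of P - B (drift before escalation) and e for the mean of A - P (change after the step). The stated baseline gives d + e; a baseline at P gives e. As an invented single case, a subject at +22 ms before escalation who rises a further 10 ms has 22 + 10 = 32 ms and falls in the class above 30 ms, while the change since escalation is 10 ms.

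**Illustration.** The documents give neither d nor the SD of within-subject change. Assumed: normal changes, the same SD from either baseline, SD 10, 12 or 15 ms, and drift from -10 to +15 ms. Then

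P(change > 30 ms) = 1 - Φ((30 - m)/SD), with m = d + e from study baseline and m = e from the escalation-day ECG.

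For d = 10, e = 0 and SD = 10, this is 1 - Φ(2.0) = 2.3% from study baseline and 1 - Φ(3.0) = 0.1% from the escalation-day ECG.

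Share above 30 ms when 200 mg has no effect (e = 0):

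| Baseline and drift | SD 10 | SD 12 | SD 15 |
|---|---|---|---|
| Study baseline, d = 0 | 0.1% | 0.6% | 2.3% |
| Study baseline, d = +5 | 0.6% | 1.9% | 4.8% |
| Study baseline, d = +10 | 2.3% | 4.8% | 9.1% |
| Study baseline, d = +15 | 6.7% | 10.6% | 15.9% |
| Escalation-day ECG, any d | 0.1% | 0.6% | 2.3% |

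The distortion can also run the other way. With d = -10 and e = +10, the mean change from study baseline is 0 and the flagged shares are 0.1%, 0.6% and 2.3%. From the escalation-day ECG the mean is +10 and the shares are 2.3%, 4.8% and 9.1%. With no drift the two baselines agree.

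The class above 60 ms hardly moves: with e = 0 its share is at most 0.14% (d = +15, SD 15) from study baseline.

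**Absolute limits.** Values above 450, 480 or 500 ms need no subtraction. Whether one counts as *new* after escalation needs a reference, and SAP 2.7.4.1 does not define the word for a split period.

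**The case against.** The strongest reply is that the planned tables already allow the separation at group level. The escalation-day pre-dose ECG is a scheduled assessment, and nothing excludes it from the by-timepoint summaries or the listings. In subjects with both readings, the mean change after escalation minus the mean change at the escalation visit equals the mean within-subject change, because the common baseline cancels. This stands for the mean, provided the tables are laid out relative to escalation and over the same subjects, which the SAP does not say. It does not give the spread of the within-subject change or the counts above 30 and 60 ms, because categories cannot be subtracted.

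A second reply is that change from the untreated state is a legitimate safety measure, and that the QTcF rule in Protocol 6.6.3.1 is itself written against baseline. This stands in full. A baseline taken on 80 mg would remove any change that 80 mg had caused, so it cannot replace the existing one.

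A third is that the pre-dose reading is an imperfect reference. Protocol 8.4.3 says that ECGs after Week 2 need no fixed time after dosing, so a pre-dose baseline would be compared with readings at varying times since dose. This also stands, as a caveat to print with the table.

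A reader might go further and infer that the SAP credits drift on 80 mg to 200 mg, that its tables cannot separate the two at all, or that an abnormality first seen on 80 mg is counted again as *new*. The documents do not support these readings. The SAP attributes no change to 200 mg and plans no ECG test. Group drift is visible from the split, and *new* is left undefined rather than defined so as to count twice.

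**Conclusion.** The point holds as a gap in a descriptive safety analysis, and it should be closed. It is not an error that invalidates a table. The SAP gives one ECG baseline, before treatment, and the after-escalation tables inherit it because no other exists; SAP 2.7.4.1 does not say so in words. Those changes and the 30 and 60 ms classes then mix earlier drift, in either direction, with the change after the step to 200 mg.

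The size is unknown. Under the assumed ranges with no effect of 200 mg, up to 15.9% of escalated subjects would be flagged above 30 ms from study baseline, against at most 2.3% from the escalation-day ECG. With no drift the difference is nil. The number of subjects affected depends on how many escalate, which the documents do not give. The primary endpoint is untouched.

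**What to change.** Keep the existing ECG tables against study baseline. Add to SAP 2.1.1 and 2.7.4.1:

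- For escalated subjects, a second ECG baseline: the mean of the escalation-day pre-dose triplicate or, if that is missing, the last ECG before the first 200 mg dose. Assign this reading to the pre-escalation period.
- Post-escalation change, increases above 30 and 60 ms, and newly notable values reported against this second baseline, alongside the existing tables.
- A definition of *new* for the after-escalation period as not present at the second baseline.
- A note to the table that later ECGs have no fixed time after dosing, so a pre-dose baseline does not fully remove time-since-dose effects.

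The general statement in Protocol 8.4.3 that ECGs after Week 2 need no fixed post-dose time, and its own requirement for a 2 to 3 hour reading on the escalation day, should be reconciled when this is written.

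The cost is SAP wording, one derived variable and one more table. The data are already collected. The wording should be settled before the escalated-period ECG tables are produced.
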